9.1.2 Intensity of Adverse Events

The intensity of clinical AEs is graded on a three-point scale: mild, moderate, severe, and reported on specific AE pages of the eCRF.

If the intensity of an AE worsens during study drug administration, the AE will be closed and a new AE with enhanced severity will be generated in the eCRF. If the AE lessens in intensity, no change in the severity is required.

If an AE occurs during a washout or placebo run-in phase and afterwards worsens during the treatment phase, a new AE page must be filled in with the intensity observed during study drug administration.

Mild: Event may be noticeable to subject/patient; does not influence daily activities; usually does not require intervention.

Moderate: Event may make subject/patient uncomfortable; performance of daily activities may be influenced; intervention may be needed.

Severe: Event may cause noticeable discomfort; usually interferes with daily activities; subject/patient may not be able to continue in the study; treatment or intervention is usually needed.

A mild, moderate or severe AE may or may not be serious. These terms are used to describe the intensity of a specific event (as in mild, moderate, or severe myocardial infarction). However, a severe event may be of relatively minor medical significance (such as severe headache) and is not necessarily serious. For example, nausea lasting several hours may be rated as severe, but may not be clinically serious. Fever of 39 °C that is not considered severe may become serious if it prolongs hospital discharge by a day (see Section 9.2.1.2). Seriousness rather than severity serves as a guide for defining regulatory reporting obligations.

9.1.3 Relationship to Study Drug

Adverse events should be assessed by the investigators as to whether or not there is a reasonable possibility of causal relationship to the study drug and reported as either related or unrelated.

Related to study drug: This category applies to any AE (serious or not) that appears to have a reasonable possibility of causal relationship to the use of the study drug (i.e., a relationship cannot be ruled out). Guidelines to determine whether an event might be considered related include (but are not limited to) the following:

- The event occurred in close temporal relationship to study drug administration.
- The event abated (diminished) or disappeared when treatment with the study drug was down-titrated, interrupted, or discontinued.
- The event re-occurred when treatment was re-introduced.
- Environmental factors such as clinical state and other treatments could equally have caused the event.

Related AEs should be considered as one of the following categories:

Definite	A clinical event, including laboratory test abnormality, occurring in a plausible time relationship to drug administration, and which cannot be explained by concurrent disease or other drugs or chemicals. The response to withdrawal of the drug (de-challenge) should be clinically plausible. The event must be definitive pharmacologically or phenomenologically, using a satisfactory re-challenge procedure if necessary.
Probable	A clinical event, including laboratory test abnormality, with a reasonable time sequence to administration of the drug, unlikely to be attributed to concurrent disease or other drugs or chemicals, and which follows a clinically reasonable response on withdrawal (de-challenge). Re-challenge information is not required to fulfill this definition.
Possible	A clinical event, including laboratory test abnormality, with a reasonable time sequence to administration of the drug, but which could also be

explained by concurrent disease or other drugs or chemicals. Information on drug withdrawal may be lacking or unclear.

Unrelated to study drug: This category applies to any AE (serious or not) that does not appear to have a reasonable relationship to the use of study drug (see above guidelines).

Unrelated AEs should be considered as one of the following categories:

Unlikely	A clinical event, including laboratory test abnormality, with a temporal relationship to drug administration which makes a causal relationship improbable, and in which other drugs, chemicals or underlying disease provide plausible explanations.
Unrelated	A clinical event, including laboratory test abnormality, which is clearly not related to drug administration.

9.1.4 Reporting of Adverse Events

All AEs occurring from the (first) dose administration and up to Follow-Up must be recorded on specific AE pages of the eCRF (note: only AEs for randomized subjects/patients will be recorded in the eCRF) see also Section 8.3.2.1.

9.1.5 Follow-up of Adverse Events

Adverse events must be followed until resolution, stabilization or up to EOS. Adverse events assessed as related must be followed until resolution, stabilization or to a maximum of 28 days after the EOS.

9.2 Serious Adverse Events

9.2.1 Definitions

9.2.1.1 Serious Adverse Events

A SAE is defined by the ICH guidelines as any AE fulfilling at least one of the following criteria:

- Results in death.
- Is life-threatening. Life-threatening refers to an event in which the subject/patient was at risk of death at the time of the event. It does not refer to an event that hypothetically might have caused death if it were more severe.
- Requires subject's/patient's hospitalization or prolongation of existing hospitalization.
- Results in persistent or significant disability or incapacity.
- Is a congenital anomaly or birth defect.
- Is medically significant or requires intervention to prevent at least one of the outcomes listed above.

Important medical events that may not immediately result in death, be life-threatening, or require hospitalization may be considered as SAEs when, based upon appropriate medical judgment, they may jeopardize the subject/patient and may require medical or surgical intervention to prevent one of the outcomes listed in the definitions above.

The reference safety document to assess whether or not an SAE should be reported by the Sponsor to Health Authorities, IECs/institutional review boards (IRBs) and investigators in an expedited fashion is the Investigator's Brochure.

9.2.1.2 Pregnancy

All initial reports of pregnancy, including pregnancy outcome (follow-up) in female subjects/patients or in partners of male subjects/patients, must be reported to QPS safety unit (QPS SU) by the Investigator within 24 hours of his/her knowledge of the event using a Pregnancy Form.

The Investigator will contact the subject/patient at the expected time of delivery for follow-up. Abnormal pregnancy outcomes (e.g., induced abortion, stillbirth, neonatal death, congenital abnormality, birth defect) are considered SAEs and must be reported using the Serious Adverse Event Form.

9.2.1.3 Hospitalization – Prolongation of Existing Hospitalization

Hospitalization is defined as an overnight stay in a hospital unit and/or emergency room.

An additional overnight stay defines a prolongation of existing hospitalization.

The following is not considered an SAE and should be reported as an AE only:

- Treatment on an emergency or outpatient basis for an event not fulfilling the definition of seriousness given above and not resulting in hospitalization.

The following reasons for hospitalizations are not considered AEs, and therefore not SAEs:

- Hospitalizations for cosmetic elective surgery, social and/or convenience reasons.
- Standard monitoring of a pre-existing disease or medical condition that did not worsen, e.g., hospitalization for coronary angiography in a patient with stable angina pectoris.
- Elective treatment of a pre-existing disease or medical condition that did not worsen, e.g., hospitalization for chemotherapy for cancer, elective hip replacement for arthritis.

9.2.1.4 Serious Adverse Events Related to Study-mandated Procedures

Such SAEs are defined as SAEs that appear to have a reasonable possibility of causal relationship (i.e., a relationship cannot be ruled out) to study-mandated procedures (excluding administration of study drug) such as discontinuation of subject's/patient's previous treatment during a washout period, complication of a mandated invasive procedure (e.g., blood sampling, heart catheterization), car accident on the way to the hospital for a study visit, etc.

9.2.2 Reporting of Serious Adverse Events

9.2.2.1 Before Study Drug Initiation

Serious adverse events occurring after signature of the Informed Consent and up to study drug initiation must be reported to the QPS SU.

9.2.2.2 During Study Drug Administration

All SAEs regardless of causal relationship must be reported, including those related to study-mandated procedures. These SAEs occurring during study drug administration, i.e., between study drug initiation and EOS, are defined as treatment emergent SAEs.

These SAEs are reported on SAE forms and also on AE pages in the eCRF. Therefore, they are entered both in the drug safety and clinical databases, and must be reconciled before study closure.

9.2.2.3 After Study Drug Administration

New SAEs, including those related to study-mandated procedures, occurring after study drug administration, i.e., until EOS, must be reported.

All SAEs occurring after study drug administration until Follow-Up must be recorded on an SAE form and as AEs in the eCRF. Therefore, these treatment-emergent SAEs are entered both in the QPS drug safety and clinical databases, and must be reconciled before study closure.

9.2.2.4 Reporting Procedures

All SAEs must be reported by a Principal Investigator to QPS SU within 24 hours of the Investigator's knowledge of the event.

All SAEs must be recorded on SAE forms, irrespective of the study drug received by the subject/patient, whether or not this event is considered by the Investigator to be related to study drug.

These SAE forms must be sent to QPS SU. The Investigator must complete the SAE form in English (unless otherwise specified) and assess the relationship to study drug.

Such preliminary reports will be followed by detailed descriptions that should include copies of hospital case reports, autopsy reports, hospital discharge summaries and other documents when requested and applicable. Follow-up information about a previously reported SAE must also be reported within 24 hours of receiving it. QPS SU may contact the Investigator to obtain further information.

Suspected (considered related to the study drug) and Unexpected (not previously described in the reference safety information), Serious Adverse Reactions (SUSARs) will be expedited by QPS SU to Health Authorities, IEC/IRB and investigators, as appropriate. SUSARs will not be subject to systematic unblinding.

9.2.3 Follow-up of Serious Adverse Events

Serious adverse events still ongoing at the EOS visit must be followed until resolution or stabilization or until the event is otherwise explained or referral to appropriate medical care.

New SAEs occurring at any time after the EOS or after the 28-day follow-up period after study drug discontinuation (whichever comes first) may be reported to QPS SU within 24 hours of the Investigator's knowledge of the event, if felt appropriate by the investigators.

Such information will only be entered into the drug safety database and hence will not affect study closure.

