9 SAFETY DEFINITIONS AND REPORTING REQUIREMENTS

9.1 Adverse Events

9.1.1 Definitions of Adverse Events

Any untoward medical occurrence in a patient or clinical investigation subject administered a pharmaceutical product and which does not necessarily have a causal relationship with this treatment. An AE can therefore be any unfavorable and unintended sign (including an abnormal laboratory finding), symptom, or disease temporally associated with the use of a medicinal (investigational) product, whether or not related to the medicinal (investigational) product (International Council for Harmonization (ICH) E6; Section 1.2).

A treatment-emergent AE is any AE temporally associated with the use of a study drug, whether or not considered related to the study drug.

Adverse events include:

- Exacerbation of a pre-existing disease.
- Increase in frequency or intensity of a pre-existing episodic disease or medical condition.
- Disease or medical condition detected or diagnosed after study drug administration even though it may have been present prior to the start of the study.
- Continuous persistent disease or symptoms present at baseline that worsen following the start of the study.
- Lack of efficacy in the acute treatment of a life-threatening disease.
- Events considered by the Investigator to be related to study-mandated procedures.
- Abnormal assessments, e.g., ECG, vital signs or physical examination findings, must be reported as AEs if they represent a clinically significant finding that was not present at baseline or worsened during the course of the study.
- Laboratory test abnormalities must be reported as AEs if they represent a clinically significant finding, symptomatic or not, which was not present at baseline or worsened during the course of the study or led to dose reduction, interruption or permanent discontinuation of study drug.

Adverse events do not include:

- Medical or surgical procedure, e.g., surgery, endoscopy, tooth extraction, transfusion. However, the event leading to the procedure is an AE. If this event is serious, the procedure must be described in the SAE narrative.
- Pre-existing disease or medical condition that does not worsen.
- Situations in which an adverse change has not occurred, e.g., hospitalizations for cosmetic elective surgery or for social and/or convenience reasons.

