10.4 Safety and Tolerability Parameters

Definitions of the safety and tolerability parameters are described in Section [8.11.2](#).

The safety set is used to perform all safety analyses.

The medical history is coded using the latest version of MedDRA and listed.

All AEs and SAEs are coded using the latest version of MedDRA.

The treatment-emergent AEs are tabulated by system organ class (SOC), and individual preferred terms within each SOC by treatment group. The number and percentage of subjects/patients who experienced AEs coded with the same preferred term and SOC will be summarized by treatment group (in descending order according to the incidence in the investigational study drug group). Adverse events will also be tabulated by severity and by relationship to study drug. Summary tables will be accompanied by individual subject/patient listings broken down by treatment group, including pre-dose events.

SAEs will be listed and summarized similarly to AEs.

Reasons for death will only be listed.

Reasons for premature discontinuation of study drug will be listed and summarized by frequency tables.

ECG variables, vital sign measurements and laboratory measurements will be summarized at each time point using mean, median, standard deviation, min, max, number of available observations, and change from baseline. Individual subject/patient listings of physical examination data, ECG data, vital signs data, physical examination data, immune reactions, injection site reactions, concomitant medication/therapy and laboratory measurements will be provided.

Standard numeric laboratory parameters are presented in the units supplied. If needed, a conversion will be made to standard units.

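### Section 9.2.3 makes late SAEs optional and safety-database-only from 28 days after an undefined study drug discontinuation, while 9.1.4 and 9.2.2.2 to 9.2.2.4 require them with no 28-day limit

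*Protocol*

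**What the plan says.** Protocol section 9.2.3 covers new SAEs arising late in the study. After EOS, or "after the 28-day follow-up period after study drug discontinuation (whichever comes first) may be reported to QPS SU", if the investigators think it appropriate. It adds: "Such information will only be entered into the drug safety database and hence will not affect study closure".

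Four other sections cover some or all of the same period and contain no 28-day limit:

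- Section 9.1.4: "All AEs occurring from the (first) dose administration and up to Follow-Up must be recorded on specific AE pages of the eCRF".
- Section 9.2.2.2: "These SAEs occurring during study drug administration, i.e., between study drug initiation and EOS, are defined as treatment emergent SAEs". They are entered in both the safety and the clinical database and reconciled.
- Section 9.2.2.3: "All SAEs occurring after study drug administration until Follow-Up must be recorded on an SAE form and as AEs in the eCRF". Again both databases are used and reconciled.
- Section 9.2.2.4: "All SAEs must be reported by a Principal Investigator to QPS SU within 24 hours" of the investigator learning of the event.

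No section says which rule prevails. *Study drug discontinuation* is not defined, and none of the visit schedules (Tables 5-1 to 5-3) contains a 28-day follow-up period after it. The other 28-day limit on adverse events, in section 9.1.5, is a different rule: it runs from EOS and concerns how long related events are followed.

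**The concern.** Adverse events are a primary endpoint in all parts (Protocol 8.1.1). SAP section 4.2 takes its data from the eCRF and from external laboratory and deviation data; it does not name the drug safety database. If a site treats 9.2.3 as the rule for late events, an SAE before EOS could go unreported, or could reach the safety unit and never enter the eCRF. Either way it would be missing from the treatment-emergent SAE tables, although 9.2.2.2 classes it as treatment-emergent. The SAP's own definition of a treatment-emergent event (7.7.3.3) has no 28-day cut-off and would not exclude it; the risk is that the record never reaches the analysis.

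The timing is not trivial for this product. The protocol describes 28 days as Tmax plus one half-life (6.2.1, 8.7.1), so on a last-dose reading the optional period starts while drug is still present. Expedited reporting by the safety unit (9.2.2.4) also depends on the event being reported.

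Scheduled Safety Review Committee data cuts are not affected. They use data to 14 days (Part 1), 21 days (Part 2; section 10.9 says 14) and 28 days after the last dose (Part 3), all on or before the 28-day point (8.6, 8.7.1, 10.9).

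**Working it through.** **1. The sections side by side**

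| Protocol section | Period covered | Obligation | Where recorded |
|---|---|---|---|
| 9.1.4 | First dose to Follow-Up | Mandatory | eCRF |
| 9.2.2.2 | Drug initiation to EOS | Mandatory | Both databases, reconciled |
| 9.2.2.3 | After administration to EOS/Follow-Up | Mandatory | Both databases, reconciled |
| 9.2.2.4 | No limit stated | Mandatory, within 24 hours | SAE form to safety unit |
| 9.2.3 | From the earlier of EOS and 28 days after discontinuation | Optional | Safety database only |

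Wherever the 28-day point falls before EOS, 9.2.3 and the other sections give different instructions for the same event.

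**2. What discontinuation could mean**

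- *Last dose.* The 28-day point then precedes EOS for every subject on schedule.
- *Early stopping of dosing only.* This is how the protocol mostly uses the word for study drug. Section 9.1.1, for example, speaks of laboratory abnormalities that "led to dose reduction, interruption or permanent discontinuation of study drug". Section 10.4, however, adds a qualifier: "Reasons for premature discontinuation of study drug will be listed and summarized by frequency tables". That leaves the unqualified word open.
- *Administration taken to run to EOS*, as the wording of 9.2.2.2 allows. There is then no conflict, and the 28-day clause does nothing. This reading sits badly with 9.2.2.3, which speaks of events after administration and before EOS.

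**3. Days under conflicting instructions, last-dose reading**

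The documents give no figure of their own to reproduce. Inputs from Protocol 8.2 and Tables 5-1 to 5-3: single dose on Day 1 and EOS on Day 90 (±3) in Parts 1 and 2; last dose on Day 85 and EOS on Day 169 (±5) in Part 3 on the MD1 schedule.

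Formulas: 28-day end = last dose day + 28; gap = EOS day − 28-day end; share = gap ÷ (EOS day − last dose day).

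- Parts 1 and 2: 1 + 28 = Day 29; 90 − 29 = 61 days; 90 − 1 = 89; 61/89 = 69%. With EOS at 87 to 93, the gap is 58 to 64 days.
- Part 3, MD1: 85 + 28 = Day 113; 169 − 113 = 56 days; 169 − 85 = 84; 56/84 = 67%. With EOS at 164 to 174 and dosing on Day 85, the gap is 51 to 61 days. Counted from the first dose: 56/(169 − 1) = 56/168 = 33%.

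MD2 may use a different dosing frequency, so its gap cannot be computed.

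**4. Early-stopping reading**

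The single-dose parts are essentially unaffected. A Part 3 subject whose last dose was on Day 1, 29 or 57 would reach the 28-day point on Day 29, 57 or 85. If followed to Day 169, the gap is 169 − 29 = 140, 169 − 57 = 112 or 169 − 85 = 84 days. These are upper figures: sections 8.8.3 and 12.1.9 bring the EOS assessments forward for subjects who leave the study, so the gap applies mainly to those who stop dosing but stay in follow-up.

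**The case against.** The strongest reply is that the large figures depend on the last-dose reading, while the protocol more often uses the word for early stopping; on that reading few subjects are affected. This stands, and it is why the day counts are conditional. It does not remove the point: a mandatory safety rule should not depend on which meaning a site chooses, and three centres are listed.

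Second, the schedules lower the risk. The AE/SAE row runs continuously from dosing in Tables 5-1 and 5-2, and is marked at every column from Day 1 to Day 169 in Table 5-3. Events will therefore be asked about after the 28-day point. This is correct. It also shows that collection to EOS is what the schedules expect, which supports the direction of the fix.

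Third, a permissive *may* does not cancel a *must*: a site that follows 9.1.4 and 9.2.2.2 to 9.2.2.4 also complies with the reporting sentence of 9.2.3. That is fair for the reporting sentence. It fails for the next one, which sends such information only to the safety database and so contradicts 9.1.4 and 9.2.2.3.

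Fourth, 9.2.2.4 has no end date, so it would still differ from 9.2.3 for events after EOS even if the 28-day limb were removed. Read with 9.2.2.2 and 9.2.2.3, though, 9.2.2.4 is a procedure for events up to EOS. On that reading it conflicts with 9.2.3 inside the window, and the deletion resolves this.

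Finally, comparing two databases cannot find an SAE that is in neither. That limit is real, and the check proposed below allows for it.

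**Conclusion.** The contradiction is real and lies in current protocol text. On the last-dose reading, each subject on schedule spends 61 of 89 post-dose days in Part 2 (69%), and 56 of the 84 days after the last dose in Part 3 under MD1 (67%), under instructions that disagree on whether an SAE must be reported and where it is recorded. On the early-stopping reading, few subjects are affected, mainly in Part 3. If administration is taken to run to EOS, none are.

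Confidence is moderate because the documents do not settle the intended meaning. The figures measure exposure to the conflict and do not estimate lost events. Part 1 had the same 61-day window on the last-dose reading, but section 6.1.3 reports it concluded with no SAE, and nothing in the documents suggests that an SAE has been lost in any part. The point is still worth correcting, because it bears on the completeness of a primary safety endpoint and the correction is small.

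**What to change.** Reconcile 9.2.3 with 9.1.4 and 9.2.2.2 to 9.2.2.4. The direct way is to delete the 28-day limb and the earlier-of rule from 9.2.3, so that optional, safety-database-only reporting begins only after EOS. This removes the conflict on the last-dose reading and changes little or nothing on the other two.

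Within the reconciliation that 9.2.2.2 and 9.2.2.3 already require, confirm that every SAE with onset up to EOS is in both databases. Because that comparison cannot reveal an event missing from both, also check the source records of AE questioning at visits after the 28-day point, as part of the source data verification in 12.1.3.2. SAP section 3.1 has lock and unblinding done part by part, so do this before the lock of each part still open.

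Cost: one protocol amendment (12.1.1), with ethics committee and health authority approval if it is judged substantial (12.1.1.2), plus the check. No new visits or data collection are needed.
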